However, PLATO included only patients with acute coronary syndromes. As a result, the average patient age was 62 years. The average patient age for the TRACTOR Migraine Pilot Study cohort should be around 30 years. Historically, blood-thinning agents have a much higher propensity for causing bleeding in the older population. In addition, all patients in the PLATO trial were on dual antiplatelet therapy (with aspirin), which also increases the bleeding risk. In the TRACTOR Migraine Trial subjects will not be taking aspirin concurrently. The bleeding risks in PLATO were statistically higher, but not clinically different from that in the clopidogrel population. We had no bleeding complications in a similar migraine population, in our published clopidogrel trial.¹⁴

Other Potential Risks:

In PLATO²⁸ there were no serious clinical risks associated with the other observed side effects of the drug. Dyspnea was self-limited and mild in most. Elevation of serum uric acid and creatinine was not a clinically important issue, and in the TRACTOR Migraine Pilot will

be less important in a younger, healthier population. The bradyarrhythmic episodes noted in PLATO were also not clinically important or apparent.

Outcomes in the TRACTOR Migraine Trial will be compared to historical data from prior studies and drug manufacturing data to identify any new, unexpected adverse events or outcomes. The Executive Committee of the Trial will review all reports of adverse events.

POTENTIAL BENEFITS:

This is an observational study of the off-label use of Brilinta/ticagrelor as a primary therapy for treatment of migraine headache. In a previous study of 15 patients with severe migraine treated with clopidogrel¹⁴, >80% had improvement or complete resolution of symptoms. It is unknown if Brilinta/ticagrelor will benefit any individual subject.

ALTERNATIVES:

Subjects may choose not to participate in this study. Subjects may continue to work with their Neurologist using other preventive headache therapies such as Onabotulinumtoxin A, beta-blockers, topiramate, divalproex/sodium valproate, calcium channel blockers, and others including non-medication management.^{33,34}

WITHDRAWAL OF SUBJECTS:

There may be circumstances in which a participant may need to withdraw from the TRACTOR Migraine Trial. These may include either Serious or Important Adverse Events (as listed above), a change in health status (including need for urgent surgical or medical intervention, or unanticipated pregnancy), or non-compliance with the protocol. Non-compliance would be defined as recurrent failure to take the medication as directed, failure to keep protocol appointments, or repeated failure to enter headache log information despite reminders from the local study coordinator.

Any other serious adverse event, which might require discontinuation of the study drug, would require documentation of the issue by the local study team, with formal consultation with the Principal Investigator. An electronic Patient Withdrawal Form would need to be completed by the Principal Investigator. Any adverse event leading to subject withdrawal will require documented discussion by the Executive Committee, and a follow-up assessment by the local study team, to confirm the participant's return to baseline health status.

Once withdrawn from the TRACTOR Migraine Trial for medical reasons, all efficacy data collected to date will be maintained, but no further data will be collected. Any participant who completes the daily headache logs for at least two weeks while on treatment, but who does not complete the full four weeks of the study period, will be classified according to their current response status (LOCF), regardless of whether or not they completed the required therapy (see Outcomes Assessment).

Should a participant choose to withdraw consent for the TRACTOR Migraine Trial, at any time during the monitoring period, for reasons other than an adverse event, the participant must contact the principal investigator, who will complete an electronic Patient Withdrawal

Form. In such a circumstance, efficacy data already collected will no longer be eligible for review. However, safety data up to the point of participant withdrawal will be reviewable for the final data analysis.

MEDICAL MONITORING

The Principal Investigator and his designees will have the primary responsibility of monitoring participant safety. All potential issues of participant safety will be reported to the Executive Committee, which will be comprised of all of the TRACTOR Migraine study Investigators. The Executive Committee will serve the function of the Data and Safety Monitoring Board for the TRACTOR Migraine Trial. This group will meet monthly, after enrollment of the first patient, and will review all safety data on an on-going basis and all SAE's within 48 hours. Enrollment, clinical outcomes and safety data will be reviewed for all patients after 20 patients have been enrolled.

DATA HANDLING AND RECORD KEEPING

Confidentiality:

Information about study subjects will be kept confidential and managed according to the requirements of the Health Insurance Portability and Accountability Act of 1996 (HIPAA). Those regulations require a signed subject authorization informing the subject of the following:

- What protected health information (PHI) will be collected from subjects in this study
- Who will have access to that information and why
- Who will use or disclose that information
- The rights of a research subject to revoke their authorization for use of their PHI.

In the event that a subject revokes authorization to collect or use PHI, the investigator, by regulation, retains the ability to use all information collected prior to the revocation of subject authorization. For subjects that have revoked authorization to collect or use PHI, attempts should be made to obtain permission to collect at least vital status (i.e. that the subject is alive) at the end of their scheduled study period.

Source Documents:

All source data, whether participant demographic information, notes from participant office visits, or participant entered headache log information will be stored in a database on a HIPAA compliant, secure server at Columbia University Medical Center. Transcranial Doppler studies will be recorded and stored in both .pdf and original format. Pharmacy records covering distribution medication will be kept at the Study Research Pharmacy. Baseline laboratory results and PRU testing results will be entered into the study database, and copies of the original documentation will be scanned into a file on the Columbia University Server.

Study Data:

All participant/study related information will be stored in a database on secure server at Columbia University Medical Center. At the time of enrollment, the Study Coordinator will

assist the participant in entering her/his personal demographic information into the database, through a data entry page on the TRACTOR Migraine Trial Website. This webpage will also be housed on the Columbia University Server.

All daily headache log data will be entered (e-CRF's) directly by the participant via computer, smartphone, or on paper through the REDCap Survey Tool, housed on the Columbia University Server.

Record Retention:

The local study investigator will maintain all study records according to ICH-GCP and applicable regulatory requirement(s).

STUDY MONITORING, AUDITING AND INSPECTING

Monitoring Plan:

The Principal Investigator/IND Sponsor (PI) will ensure that the study protocol is followed, the data is accurate and the research subjects are safe. Safety data will be reviewed by the PI, or by his designee, as soon as it is received. Safety data will also be monitored by the Executive Committee (EC), which will review safety data and make recommendations regarding continuation, termination, or modification of the study. The EC will formally review the safety data, enrollment, and clinical outcome data after the first 20 subjects have been treated and will review all serious adverse events within 48 hours.

A dedicated Study Coordinator will review 100% of source documentation/data collected for accuracy, including all safety data. The regulatory binder, along with other essential study documents, will also be reviewed to ensure that it is complete and up to date. The first review will occur after the first subject is enrolled and will continue weekly with new enrollments. Any discrepancies will be discussed with relevant study personnel for clarification and/or correction.

The Study Coordinator will be responsible for the monitoring and day-to-day running of the trial. Her/his responsibilities will include:

- scheduling all appointments for Transcranial Doppler
- obtaining consent for participants on the day of their initial visit
- checking the data against source documentation for all participants to ensure data accuracy and integrity
- tracking blood test results for baseline evaluation and entering laboratory data into the study database
- scheduling additional study visits
- tracking participant compliance with the daily headache logs

Appendix 1:

Trial Schedule: (see attached TRACTOR Migraine Trial Flow Sheet in Appendix 2)

Study Visit #1: At the time of the first visit, study coordinator/investigators will discuss trial and subject eligibility for participation based on migraine headache frequency. The coordinator will collect all demographic information required for the study. Participant will receive explanation of the additional testing required for trial participation. After patient has been given an opportunity to ask questions, a screening consent will be signed to perform this testing. Participant will receive a Patient Study Number. Transcranial Doppler study will be performed. If negative for right to left shunt, participant will be sent back to the referring physician for on-going clinical care. If positive for right to left shunt (Spencer Grade ≥ 2) participant will be eligible to continue in the trial. The trial will be explained in detail, including participant responsibilities, and the patient will receive written study materials. A complete TRACTOR Migraine Headache Trial consent will be signed. The participant will receive a test e-mail/text message and must demonstrate the ability to answer the headache log questions. A Quality of Life Survey will be taken. Laboratory screening is done. End of visit.

Study Phase 1:
(28 Days) Within 72 hours of the laboratory evaluation, participant will be notified of results of laboratory testing and ability to continue participation. She/he will begin to receive daily reminders (e-mail/text message) to log-in to answer the headache log questions. A follow-up appointment will be scheduled within 7 days of the completion of 28 days of headache monitoring.

Study Day 29: Headache log entries will be reviewed by the Study Coordinator to determine final eligibility for trial based on the number of headache days documented.

Study Visit #2: Must occur within seven days of completion of baseline headache log. Participant will return to receive her/his medication. She/he will receive a loading dose of 180 mg of Brilinta/ticagrelor and an additional 70 tablets and will again review the responsibilities for participation with the coordinator. The participant will be observed for 30 minutes after taking the first medication dose.

Study Phase 2:
(28-35 Days) Participant will receive reminder text message/e-mail to take daily study medication, and to log-in to answer the headache log questions. Participant will take Brilinta/ticagrelor 90 mg twice daily for 28-35 days. Participant will receive instructions for PRU testing.

PRU Testing: (> 7 days on drug)	Participant will go to local laboratory or to study center for blood testing of platelet inhibition.
Study Visit #3:	Within 7 days of completion the 28 th day of the study medication participant will return to meet with the study coordinator to review the results of the therapy, to return unused medication, and to review any adverse events. If no perceived benefit, participation is completed. If subject has had a clinical benefit, options for on-going therapy with additional headache log entries will be discussed. Participant will complete a follow-up Quality of Life questionnaire.
Continued Access (56-63 days):	If eligible, participant will continue to take Brilinta/ticagrelor for an additional 2 months. She/he will continue to receive daily e-mail/text message reminders to log-in to record headache data.
Study Visit #4:	Within 7 days of the 56 th day of study medication, participant will return to meet with the study coordinator to review the results of the therapy, to return unused medication, and to review any adverse events. Participant will complete a follow-up Quality of life questionnaire. Study is complete.

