We propose a prospective, open-label, single-arm pilot study treating 40 subjects to assess the hypothesis that P2Y12 inhibition with Brilinta/ticagrelor (90 mg PO twice a day) reduces episodic and/or chronic migraine headache symptoms in patients with right to left shunt. There will be no randomization or blinding of therapy. The study drug will be provided, free of charge, by the manufacturer, Astra-Zeneca. All subjects will be treated with the same medical regimen, and will be treated at Columbia University Medical Center or one of Principal Investigators external offices. All subjects will have an initial visit that will include the completion of a screening questionnaire (inclusion/exclusion criteria), informed consent, transcranial Doppler screening, laboratory blood testing by venipuncture (approximately 15 cc of blood = 1 tablespoon), and instruction on the use of the daily headache log (see Appendix 1, Appendix 2). Over the next 28 days, the subjects will receive an e-mail/text reminder daily with a link to complete the headache log (see below). At a second study visit, following completion of the first baseline month, the study staff will review the subject's headache log material, will release those subjects with insufficient headache days in the screening month, will assign the remaining/eligible subjects to either the episodic or chronic migraine cohort, will distribute the study drug, will administer the Brilinta/ticagrelor loading dose, and will review the medication's proper use. After 7 days of treatment with Brilinta/ticagrelor, while still on therapy, subjects will be sent for additional laboratory testing (PRU test < 10 cc of blood by venipuncture). At the completion of the 28 days (+7 days) on Brilinta/ticagrelor, each subject will have a follow-up study visit within 7 days, before discontinuing medication. At the third study visit, headache logs will be reviewed with the study staff, results will be discussed, remaining medications and empty bottles will be returned, and adverse events will be reviewed. Headache frequency while on Brilinta/ticagrelor will be compared with the documented baseline for each subject. If the Brilinta/ticagrelor therapy was effective (> 50% reduction in monthly headache days), the subject could elect to continue therapy for an additional two months, while continuing to complete daily headache logs.

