- Active bleeding from any site
- Active peptic ulcer disease or upper gastrointestinal (GI) bleeding within six (6) months
- Migraine onset after 50 years of age
- Renal impairment: Creatinine Clearance < 60 cc/min
- Severe hepatic impairment with total bilirubin > 3.0 mg/dL
- Thrombocytopenia with platelet count < 100,000 / μ L
- History of intracranial hemorrhage
- Contraindications to blood thinner therapy or history of major bleeding episode while taking blood thinner therapy

- Need for chronic oral anti-coagulation therapy (i.e. Atrial Fibrillation)
- Need for chronic anti-platelet therapy (i.e. DE Stent), including daily aspirin use
- Need for daily NSAID use
 - Need for daily carbamazepine therapy or other strong CYP3A inhibitors or potent CYP3A inducers (see Reference Medication Form).
 - Need for simvastatin or lovastatin greater than 40 mg daily
 - Symptomatic bradycardia or syncope
- Pregnancy or currently breast-feeding, or plan to become pregnant during the study period
- Planned surgery during the study time-frame
- Previously implanted PFO, ASD, pacemaker, inferior vena cava filter, or left atrial appendage closure device
- Subject is unwilling to sign the Informed Consent Form
- Subject is currently enrolled in another investigational study that has not met the primary endpoint.

Transcranial Doppler Screening:

The presence of a right to left shunt, as defined by transcranial Doppler screening (described below) is a requirement for receiving the study drug under the TRACTOR Migraine protocol. As the incidence of a right to left shunt is ~ 25% in the migraine population, in order to find 40 subjects for treatment who fulfill all of the migraine definitions, the preliminary inclusion and exclusion criteria, and who have a right to left shunt, approximately 160 subjects will need to be screened. It is anticipated that few, if any of those identified with a right to left shunt will be excluded on the basis of subsequent laboratory testing or baseline migraine screening.

Transcranial Doppler Screening:

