Participants who are treated with Botox injections, may be considered for the TRACTOR Migraine Trial, but should be warned of the small additional risk of bleeding at the site of the injection while on blood thinner therapy. This should be discussed with the potential participant, as part of the informed consent process. The study coordinator will be responsible for documentation of these discussions.

During the TRACTOR Trial, there will be no restrictions on abortive/rescue medications for migraine episodes, among the categories of drugs as follows:

- *Opiates*
- *Benzodiazepines*
- *Non-steroidal anti-inflammatories*
- *Aspirin*
- *Tylenol*
- *Triptans*
- *Caffeine*
- *Ergotamines*
- *Butalbital*
- *Anti-emetics*
- *Muscle Relaxants*

The use of abortive/rescue therapy will be documented in the daily headache log.

Headache Tracking and Treatment Phases:

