Baseline-Monitoring Phase (Phase 1): The subject will track her/his headaches daily for 28 days through an online survey tool (REDCap, licensed through Columbia University), to establish a baseline headache frequency. Each day, the subject will receive a text message/e-mail reminder to complete the daily headache log. The message will contain a link to log into the survey tool. During this phase, subjects will answer questions including presence or absence of headache symptoms, severity of headache symptoms, duration of symptoms, impact on daily activities, and use of rescue medication. Any headache lasting more than 24 hours will be counted as a second headache day. After 28 days of monitoring, the study coordinator will assess the subject's data to make sure the subject meets criteria for minimum headache days, and has been consistently performing the daily log. If the number of headache days is insufficient, the subject's participation will be completed. If the subject logs at least 6 headache days in the month, she/he will continue in the study. If the participant has been assigned to the Episodic arm of the study, but has >14 headache days in the screening month, or if the participant has been assigned to the Chronic arm of the study, but has <15 headache days in the screening month, she/he will NOT be reassigned, but will remain in the assigned group for analysis. The subject will then be treated with Brilinta/ticagrelor for a 28-35 day test period (Phase 2). The length of the test period will depend on the timing of the participant's follow-up visit after beginning treatment. The protocol window is 28+7 days.

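### No step between screening and the first dose reconfirms the exclusion criteria; Day 29 eligibility rests on headache days and log completion

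*Combined protocol and SAP*

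**What the plan says.** **When the exclusions are applied.** Under Study Subjects, patients meet the preliminary inclusion and exclusion criteria before they are offered participation. The laboratory text under Transcranial Doppler Screening has the remaining entry requirements met before Phase 1 starts.

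**What is checked after the 28-day log.**
- The Day 29 entry in Appendix 1 sets this rule: "Headache log entries will be reviewed by the Study Coordinator to determine final eligibility for trial based on the number of headache days documented".
- Headache Tracking and Treatment Phases, Phase 1: the coordinator checks that the subject "meets criteria for minimum headache days, and has been consistently performing the daily log". Then: "If the subject logs at least 6 headache days in the month, she/he will continue in the study". The next step named is treatment.
- Study Design and Statistical Procedures: at the second visit staff "will release those subjects with insufficient headache days in the screening month", assign the others to a cohort, dispense drug and give the loading dose.
- Appendix 1, Study Visit #2: "She/he will receive a loading dose of 180 mg of Brilinta/ticagrelor and an additional 70 tablets", with a review of responsibilities and a short observation period.

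**Related text.** The Preliminary Exclusion Criteria include "Need for daily NSAID use" and, under chronic antiplatelet therapy, daily aspirin. Allowed Headache Medications puts no restriction on rescue NSAIDs or aspirin and adds: "The use of abortive/rescue therapy will be documented in the daily headache log". Potential Risks argues for a lower bleeding risk than in PLATO partly because subjects will not be on aspirin at the same time. Withdrawal of Subjects says a participant may need to leave for a change in health status, including pregnancy or urgent surgical or medical need, or for non-compliance.

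**The concern.** Several exclusions describe states that can begin after screening: active bleeding, pregnancy, planned surgery, an interacting drug, daily NSAID or aspirin use. They are asked about once, a month or more before exposure. The check that Appendix 1 calls final looks at something else. A subject who comes to meet an exclusion in between can satisfy every stated condition for the loading dose.

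The exclusions most likely to change concern bleeding and drug interaction, so the first stake is subject safety. The second is interpretation: the safety set takes in everyone who receives a dose, and its bleeding outcomes are to be compared with PLATO. With 40 subjects, one bleed in someone the protocol meant to exclude would be hard to read.

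**Working it through.** **1. Interval from Visit 1 laboratory work to first dose.** Inputs from Appendix 1:
- laboratory evaluation to notice of results: 0 to 3 days (72 hours)
- baseline log: 28 days
- end of log to Visit 2: 0 to 7 days

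Shortest: 0 + 28 + 0 = 28 days. Longest: 3 + 28 + 7 = 38 days.

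The pregnancy test may be done up to 7 days before enrollment. Assuming enrollment is at Visit 1, as the order of events suggests, that test can be up to 7 + 38 = 45 days old at the first dose.

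**2. What each step in that interval checks.**

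| Step | Stated content | Exclusions asked again? |
|---|---|---|
| Phase 1 | Daily log; compliance review | Not stated |
| Day 29 | Headache days; consistent logging; coordinator contact | Not stated |
| Visit 2 | Log review, release for too few headache days, cohort, drug, loading dose | Not stated |
| Withdrawal provision | Changed health status or non-compliance | Not tied to a visit |

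The flow chart in Appendix 2 marks blood testing only at Visit 1 and the PRU visit. Review of adverse events with the subject is first listed at Visit 3, after a month of drug.

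**3. Rescue drugs against the exclusions.** Three statements sit side by side: daily NSAID need and daily aspirin are exclusions; rescue NSAIDs and aspirin are unrestricted; the risk argument assumes no concurrent aspirin. The third conflicts with the second. The first and second can coexist if daily need differs from rescue use, but no text says where one becomes the other or whether logged rescue use counts.

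**4. Size.** The documents give no rate at which subjects come to meet an exclusion. As illustration only, let q be that probability and suppose nothing is detected before dosing. The expected number among 40 is 40q, and the chance of at least one is 1 − (1 − q)^40.

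| q (assumed) | 40q | Chance of at least one |
|---|---|---|
| 1% | 0.4 | 33% |
| 2% | 0.8 | 55% |
| 5% | 2 | 87% |
| 10% | 4 | 99% |

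One subject is 1/40 = 2.5% of the safety set and 1/20 = 5% of a cohort.

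**The case against.** The sponsor can fairly answer that Day 29 is final only in the sense that headache count is the last criterion outstanding. The design section gives drug to subjects described as eligible. Subjects agree to keep all medications unchanged for two months. The surgery exclusion, and part of the pregnancy one, look forward over the study period. The flow chart has a coordinator contact at Day 29 and a meeting at Visit 2, and intercurrent illness counts as an adverse event from the start of the study. The forms named in the chart are not reproduced, so one of them could contain a recheck.

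Much of this stands, and it rules out several stronger readings that a reader might infer:
- *That the plan orders dosing of a subject known to be excluded.* It does not; it is silent, and the withdrawal provision covers a known case.
- *That headache count is the only check.* That is true of the Appendix 1 sentence, but the Phase 1 text adds consistent logging.
- *That the log itself would reveal excluded drug use.* The documents say that rescue use is recorded, not that the drug is named. The chronic-migraine threshold of 15 headache days is 15/28 = 54% of days, which is not near-daily use.
- *That excluded rescue drugs would distort the before/after headache comparison.* A drug already used in Phase 1 and continued is present on both sides.

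What the answer does not supply is a stated step that asks the question. A contact or meeting may bring a change to light, but nothing specifies that it should. An agreement at entry is not a check before dosing.

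**Conclusion.** The gap holds: for 28 to 38 days before the first dose, no step in the text reconfirms the exclusions, and a newly met one is left to a general withdrawal provision that no visit triggers. This rests on the visible text and would fall away if an unseen Visit 2 form already contains the recheck.

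The number of subjects affected is unknown. The 33% to 99% figures follow from assumed rates and from supposing no detection, so they are illustrations, not expectations. The case for the change rests on its low cost and the safety purpose of the exclusions.

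The rescue-drug texts are a separate inconsistency and must be reconciled whatever is decided about Visit 2.

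**What to change.** 1. In Appendix 1 (Study Day 29 and Study Visit #2), Study Design and Statistical Procedures, and the Phase 1 text, state that final eligibility consists of the present headache-day and logging checks together with the existing inclusion and exclusion list, asked again at Visit 2 before the loading dose. Add no test and no threshold.
2. State that subjects found ineligible are released and replaced under the existing rule in Study Subjects, which continues until 20 per cohort have been treated.
3. Reconcile Allowed Headache Medications with the daily NSAID and aspirin exclusions and with the concurrent-aspirin statement in Potential Risks, and say whether logged rescue use counts toward those exclusions. Which clinical rule applies is for the investigators.

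The cost is a wording amendment, a few minutes at an existing visit, and possibly a few subjects released after completing Phase 1.
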